# 15.2 Mature Dendritic Cells (IND#17522)

# 15.21 Background

The DC used in this study is patient's autologous dendritic cells (mDC). Dendritic cells are cells manufactured in lab from monocytes removed from patients' blood by leukapheresis. The dendritic cells need to acquire tumor antigens in order to stimulate anti-tumor immunity. Patients will be treated with DC placed into a tumor killed using cryoablation where tumor antigen exposure will occur *in vivo*.

15.22 Formulation

DCs are supplied as recently thawed cells prepared from patient material. Cells are manufactured and released by the Human Cellular Therapy Lab, Mayo Clinic Rochester. Before released for use, cells will undergo testing for sterility and potency.

15.23 Preparation and storage

mDCs will be prepared and stored at the Human Cellular Therapy Lab, Mayo Clinic Rochester according to approved SOPs included in the IND. The drug will be supplied to the appropriate administration area by personnel from the Human Cellular Therapy Lab/Immune, Progenitor, and Cellular Therapy (IMPACT) Unit.

15.24 Administration:

See Section 7.5.

15.25 Pharmacokinetic information

NOTE: this drug is a biologic made up of cells from the patient. Classical drug pharmacokinetics do not apply.

- 15.26 Potential Drug Interactions: Unknown.
- 15.27 Known potential toxicities: Unknown.
- 15.28 Drug procurement:

Drug is manufactured on site in the Immune, Progenitor, and Cell Therapeutics (IMPACT) Laboratory [contact]

# 15.3 Pneumococcal 13-valent Conjugate Vaccine (Prevnar13®)

15.31 Background:

Pneumococcal 13-valent Conjugate Vaccine (Diphtheria CRM197 Protein), is a sterile solution of saccharides of the capsular antigens of *Streptococcus pneumoniae* serotypes 1, 3, 4, 5, 6A, 6B, 7F, 9V, 14, 18C, 19A, 19F and 23F individually linked to non-toxic diphtheria CRM197 protein. Each serotype is grown in soy peptone broth.

Potency of the formulated vaccine is determined by quantification of each of the saccharide antigens, and by the saccharide to protein ratios in the individual glycoconjugates.

15.32 Formulation

Supplied as ready-to-use prefilled syringes (10 x 0.5-mL prefilled syringes per package). Pneumococcal 13-valent Conjugate Vaccine is manufactured as a liquid preparation for intramuscular injection. Each 0.5 mL dose of the vaccine is formulated to contain approximately 2.2 µg of each of *Streptococcus pneumoniae* serotypes 1, 3, 4, 5, 6A, 7F, 9V, 14, 18C, 19A, 19F, 23F saccharides, 4.4 µg of 6B saccharides, 34 µg CRM197 carrier protein, 100 µg polysorbate 80, 295 µg succinate buffer and 125 µg aluminum as aluminum phosphate adjuvant.

15.33 Preparation and storage:

Pneumococcal 13-valent Conjugate Vaccine is stored at refrigerated temperatures of 2°C to 8°C (36°F to 46°F) away from freezer compartment. DO NOT FREEZE. Discard if frozen.

15.34 Administration

Shake vigorously immediately prior to use to obtain a uniform suspension in the vaccine container. The vaccine should not be used if it cannot be resuspended. After shaking, the vaccine is a homogeneous, white suspension. Do not mix the vaccine with other products in the same syringe.

15.35 Potential Drug Interactions

Patients receiving therapy with immunosuppressive agents (large amounts of corticosteroids, antimetabolites, alkylating agents, cytotoxic agents) may not respond optimally to active immunization.

As with other intramuscular injections, Pneumococcal 13-valent Conjugate Vaccine should be given with caution to patients on anticoagulant therapy.

See complete prescribing information for information regarding coadministration of Pneumococcal 13-valent Conjugate Vaccine with other vaccines.

15.36 Known potential toxicities

There is no safety data available in the adult patient population. Please see Prevnar13® prescribing information for comprehensive toxicity data.

The following systemic events were noted within 2-3 days of the Pneumococcal 13-valent Conjugate Vaccine injection in pediatric patients: fever, irritability, drowsiness, restless sleep, decreased appetite, vomiting, diarrhea, and urticaria-like rash. The following local reactions occurred within 3 days of immunization pediatric patients: erythema, induration, tenderness and interference with limb movement.

15.37 Drug procurement

Prevnar13 will be purchased with study funds and provided free of charge to patients.

16.11 Run-in phase (Phase Ib)

Six patients will be enrolled onto Schedule 1. If at most one of these 6 patients develops a DLT during the first 3 cycles of treatment then Schedule 1 will be carried forward to the continuation phase (Phase II).

If two or more patients enrolled onto Schedule 1 develop a DLT during the first 3 cycles of treatment, then an additional 6 patients will be treated on Schedule -1 (See Section 7.2).

16.12 Continuation phase (Phase II)

Schedule of pembrolizumab, cryoablation, mDCs, and Prevnar13 will be based on the tolerability findings of the run-in phase

16.13 Adverse Event Stopping Rules

Enrollment to the trial will temporarily suspended for close examination of treatment safety and tolerability:

- at each instance of a treatment related death;
- if 2 or more of the first 6 patients develops one of the following toxicities that is considered to be possibly, probably, or definitely related to protocol treatment: a Grade 4 hematologic toxicity or Grade 3 or worse non-hematologic toxicity;
- or at any time after the first 6 patients have been enrolled, if 25% or more patients develops one of the following toxicities that is considered to be possibly, probably or definitely related to protocol treatment: a Grade 4 hematologic toxicity or Grade 3 or worse non- hematologic toxicity.

All toxicity data will be examined to assess whether changes should be made in the treatment or eligibility criteria to increase the tolerability of the treatment. All modifications to the protocol will be forwarded to the IRB for review.

# 16.2 Sample Size and accrual rate

If a cohort of 33 patients is enrolled onto the schedule carried forward into the continuation phase, a one-sided exact binomial test of proportions with significance level of 0.10 will have a 90% chance of rejecting the null hypothesis that the tumor response rate is at most 12% when the alternative hypothesis that the tumor response rate is at least 30% is true.

Thus, the minimum sample size for this trial will be 33 patients (if at most 1 DLT is seen on Schedule 1 in the run-in phase) or a maximum of 39 patients (if 2 or more DLTs are seen on Schedule 1 and at most 1 DLT is seen on Schedule -1)

It is anticipated that 2 patients per month will be enrolled onto this study with a temporarily break in enrollment after the first 6 patients are enrolled onto Schedule 1 (and if necessary after the first 6 patients are enrolled onto Schedule -1) to establish a schedule to be carried forward into the continuation phase.

# 16.3 Secondary endpoints

16.31 Safety profile:

All eligible patients that have initiated treatment will be considered evaluable for assessing the safety profile. Toxicities will be graded in terms of severity and relationship to study treatment using CTC-CAE criteria. For each patient who initiated treatment, the maximum grade of each toxicity noted during treatment will be recorded. Frequency tables will be constructed by treatment schedule.

16.32 Feasibility

A point estimate of the proportion of patients who received both intra-tumoral DC injections among those who initiated treatment will be determined. A 95% exact binomial confidence interval for this proportion will be constructed.

16.33 Clinical Benefit Rate (CBR)

Clinical Benefit Rate (CBR) is defined as the proportion of patients who have completed 6 cycles of treatment without disease progression (that is, their objective disease status is a CR, PR, or stable for 6 cycles or more) A 90% exact binomial confidence interval for this proportion will be constructed.

16.34 Progression-free survival (PFS)

Time from randomization to the first 2 consecutive evaluations approximately 6 weeks apart documenting disease progression. The distribution of progression-free survival times will be estimated using the Kaplan-Meier approach.

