# 2.2 Secondary

- 2.21 To assess the safety profile of pembrolizumab combined with cryoablation and intratumoral mDCs in patients with metastatic melanoma that have failed to respond or have stopped responding to initial therapy with a PD-1 axisblocking monoclonal antibody.
- 2.22 To determine median progression-free survival (PFS) obtained with this approach in this patient population.
- 2.23 To determine median overall survival (OS) obtained with this approach in this patient population.

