#### 6.6 Treatment start

Treatment cannot begin prior to registration and must begin ≤7 days after registration.

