#### 7.0 **Protocol Treatment**

Use actual weight or estimated dry weight if fluid retention.

Cycle length is 21 days with the exception of Cycle 1 which may be extended an additional 7 days to allow for dendritic cell production.

Dose-limiting toxicity (DLT) is defined as one of the following events occurring during the first two cycles of protocol therapy and attributed as possibly, probably, or definitely related to protocol therapy.

- Any Grade 3+ toxicity
- Grade 2 infusion reaction, acute or chronic kidney disease, or pneumonitis that does not resolve to Grade 0-1 within 3 weeks.

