# **11.0** Treatment Evaluation

# 11.1 Treatment evaluation using RECIST 1.1 guidelines

The first scan after treatment initiation will be performed at the completion of Cycle 4; scans will be then performed at the completion of every fourth cycle of treatment until disease progression is confirmed or withdrawn of consent. If a patient experiences PD yet continues protocol treatment, the next imaging should take place 2 cycles after the imaging showing PD. If that patient continues on protocol treatment, imaging should then take place every 4 cycles (See Section 4.0).

Disease progression for this protocol is defined as meeting the RECIST criteria for disease progression on two consecutive evaluations at least 6 weeks apart.

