16.35 Overall survival (OS)

Time from registration to death due to any cause. The distribution of overall survival times will be estimated using the Kaplan-Meier approach

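### As written, section 16.34 leaves death out of the PFS event, so it defines time to confirmed progression rather than progression-free survival

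*Combined protocol and SAP*

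**What the plan says.** All references are to the combined protocol and SAP. Section 16.34 defines PFS as "Time from randomization to the first 2 consecutive evaluations approximately 6 weeks apart documenting disease progression" and estimates it by Kaplan-Meier. The objective it serves is 2.22: "To determine median progression-free survival (PFS) obtained with this approach in this patient population". The next endpoint, overall survival in 16.35, is "Time from registration to death due to any cause".

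Section 11.1 gives the protocol-wide rule: "Disease progression for this protocol is defined as meeting the RECIST criteria for disease progression on two consecutive evaluations at least 6 weeks apart". On imaging, it says "The first scan after treatment initiation will be performed at the completion of Cycle 4", with later scans every fourth cycle, and "If a patient experiences PD yet continues protocol treatment, the next imaging should take place 2 cycles after the imaging showing PD".

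The test schedule in 4.1 also marks imaging at End of Tx (window of 7 days either side), and its footnote 1 allows more frequent imaging at the physician's discretion. Section 4.2 follows patients every 3 months until PD and every 6 months afterwards, and records death, for up to 5 years.

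Section 16.34 gives no censoring rule. It does not say which of the two evaluations dates the event.

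**The concern.** A quantity called progression-free survival is expected to fail at death. Section 16.34 states an event rule that does not include it, and 11.1 does not supply it. An analyst who follows the text must treat a patient who dies before two progression evaluations as censored or as never progressed. Either choice takes failures out of the event count and can only raise the curve.

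What is at stake is the meaning of a reported secondary result. In a single-arm trial, the median will be read beside published pembrolizumab figures such as those in 1.2 and 1.6, and the label would not match what was measured.

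**Working it through.** The documents state no numerical PFS assumption, so there is no PFS figure to reproduce. The check has four steps.

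**1. When can the first event occur on schedule?** The cycle is 21 days (7.0).
- First scan: 4 × 21 = 84 days (week 12 of treatment).
- Confirming scan: 84 + 2 × 21 = 126 days (week 18).
- Counted from registration, treatment "must begin ≤7 days after registration" (6.6), and 7.0 makes an exception for "Cycle 1 which may be extended an additional 7 days to allow for dendritic cell production". The latest case is 126 + 7 + 7 = 140 days (week 20), before scan windows.

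A patient who dies before the pair is complete is normally not an event. The End of Tx scan, discretionary imaging and event monitoring may yield some pairs, but none guarantees one.

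**2. Size of the effect at week 24 (illustration).** Take n = 33 (16.2), no other censoring by week 24, all progressions confirmed and dated at the first evaluation. Let F patients have failed by the week-24 scan, and let d of them be deaths before the first scan that are not counted.
- Deaths counted: PFS = 1 − F/33.
- As written, with these deaths censored: KM = 1 − (F − d)/(33 − d). Censoring at baseline or at death gives the same result, because no event precedes the first scan.

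With F = 17, PFS with deaths counted = 1 − 17/33 = 48.5%.

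| d | As written | Estimate |
|---|---|---|
| 1 | 1 − 16/32 | 50.0% |
| 2 | 1 − 15/31 | 51.6% |
| 4 | 1 − 13/29 | 55.2% |

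If these patients were instead carried as never progressed, which the missing censoring rule also permits, the estimates are 1 − 16/33 = 51.5%, 1 − 15/33 = 54.5% and 1 − 13/33 = 60.6%.

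**3. Does the median move?** Take the median as the first time the curve is at or below 50%, with the curve above 50% after the week-12 scan.
- F = 17: the median is 24 weeks with deaths counted. It stays there for d = 1 only because the estimate is exactly 50.0%, which depends on the tie convention. For d = 2 or 4 it moves to a later scan.
- F = 21: PFS with deaths counted = 1 − 21/33 = 36.4%. With d = 4, KM = 1 − 17/29 = 41.4%, and the median stays at 24 weeks.

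**4. How many early deaths are plausible?** This is an assumption. With constant hazard, P(death before week w) = 1 − 0.5^(w × 7/30.44/median OS in months).

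| Median OS | Before week 12 | Before week 18 |
|---|---|---|
| 23 months (1.6, a wider pembrolizumab population) | 8.0%, 2.6 of 33 | 11.7%, 3.9 of 33 |
| 12 months (assumed, not in the documents) | 14.7%, 4.9 of 33 | 21.3%, 7.0 of 33 |

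These are all deaths in the interval. Those already documented with a confirming pair through extra imaging would not be left uncounted.

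**Primary design.** For comparison, the design in 16.2 reproduces: with success at 7 or more responses in 33, exact one-sided alpha is 0.0930 at 12% and power is 0.9056 at 30%. PFS does not enter it.

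**The case against.** **The name implies death.** The endpoint is called progression-free survival, deaths are collected under 4.2, and an analyst may well count them. If so, the bias from omitted deaths disappears. But that analyst departs from an explicit event rule, so the text should say what is meant.

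**Confirmation is deliberate.** This stands. Section 11.1 defines progression for the whole protocol as two evaluations, and under 13.2 a patient whose first PD is not confirmed continues treatment. A reader might infer that every unconfirmed PD is a missed event and that leaving it out is itself an upward bias. The documents do not support that: under the protocol's own rule, a single PD is not yet progression. Some would not have been confirmed, so counting all of them could bias PFS downward. What is missing is only a stated handling of PD that has no later evaluation. CNS PD (which stops treatment under 13.2) and symptomatic deterioration (reported as PD under 11.45) are the obvious cases.

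**Patients are imaged when treatment stops.** This also stands. A reader might infer that only discretionary scans could rescue an early failure, but 4.1 schedules imaging at End of Tx and 11.45 asks for efforts to document objective progression after treatment stops. The limit is that the End of Tx scan need not fall 6 weeks from the first PD scan, and it cannot capture a patient who dies first.

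**The death counts are soft.** Agreed. The 23-month median comes from a wider population. Constant hazard is assumed, although entry requires ECOG 0 or 1 (3.14) and excludes active CNS metastasis (3.29i).

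**Conclusion.** The point holds on the text. Section 16.34 states an event rule that omits death and nothing else in the documents adds it, so followed as written it is time to confirmed progression. The direction is upward, conditional on the analyst following the text. The size cannot be derived from the documents. In the illustration, 1 to 4 uncounted deaths add 1.5 to 6.7 percentage points at week 24 (48.5% to between 50.0% and 55.2%), under the assumptions stated there.

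A reader might infer that the reported median must be inflated. It need not be: on a 12-week scan grid it can stay at the same scan. A reader might also extend the illustration to 7 deaths before the first scan. That exceeds the 2.6 to 4.9 obtained for week 12; 7.0 is the figure for week 18 under a 12-month median that the documents do not give.

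PFS is secondary, descriptive and untested, and the 33-patient response-rate design is unaffected. This should be fixed, but it does not threaten the primary result.

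**What to change.** Rewrite 16.34 so that it:
- defines PFS as time from registration, replacing the word randomization (a slip in a single-arm trial), to the earlier of protocol-defined confirmed progression or death from any cause;
- states whether confirmed progression is dated at the first or the second evaluation;
- censors patients alive without progression at their last tumour assessment;
- keeps the confirmation rule and states how PD with no later evaluation is handled, including CNS PD and symptomatic deterioration, for example by counting it at first documentation in a sensitivity analysis.

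Reconcile the progression wording across sections. Section 11.1 requires an interval of at least 6 weeks and 16.34 says approximately 6 weeks. Section 13.3 lists a new metastatic lesion beside the two-evaluation rule without making clear whether confirmation applies to it.

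The cost is wording only, since deaths are already collected in event monitoring. Reported PFS may be shorter than under the present text, and the sensitivity analysis will count some single PDs that might not have been confirmed.

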<sup>8 Imaging is performed at the end of Cycle 4 and then at the end of every fourth cycle of treatment (end of Cycle 8, 12, 16, etc.). Exception: if a patient has PD yet continues protocol treatment, the next imaging should take place two cycles after the imaging showing PD. If that patient continues on protocol treatment, imaging should then take place every 4 cycles.

<sup>10 Blood draw for immune monitoring will be collected prior to the start of Cycles 1-5 and prior to the start of each post-imaging cycle thereafter (prior to Cycle 9, 13, 17, etc.)

<sup>11 In addition to the research blood collection on Day 1, research blood will be collected as per Section 14 on Cycle 2, Days 2-5. The collection on Cycle 2, Day 2 should take place 2-4 hours after completion of cryoablation and mDC therapy.

<sup>12 Tumor biopsies will be performed immediately prior to cryoablation on Cycle 2 Day 1 or 2 and Cycle 3 Day 1 or 2

<sup>13 Tumor biopsies will be performed at the end of Cycle 4 after radiologic evaluation

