# 5.0 Grouping Factor

Cohort: Run-in Phase Ib Dose level 1 vs. Run-in Phase Ib Dose level -1 vs. Continuation Phase (Phase II)

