    - ii. If the positive FDG-PET at follow-up is not confirmed as a new site of disease on CT at the same evaluation, additional follow-up CT scans (i.e., additional follow-up scans at least 4 weeks later) are needed to determine if there is truly progression occurring at that site. In this situation, the date of PD will be the date of the initial abnormal PDG-PET scan.
    - iii If the positive FDG-PET at follow-up corresponds to a pre-existing site of disease on CT that is not progressing on the basis of the anatomic images, it is not classified as PD.
- The cytological confirmation of the neoplastic origin of any effusion that appears or worsens during treatment when the measurable tumor has met criteria for response or stable disease is mandatory to differentiate between response or stable disease (an effusion may be a side effect of the treatment) and progressive disease.

• Cytologic and histologic techniques can be used to differentiate between PR and CR in rare cases (e.g., residual lesions in tumor types such as germ cell tumors, where known residual benign tumors can remain.)

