# Exception: Patients who develop PD in the CNS should discontinue study treatment and go to Event Monitoring.

# **13.3** Criteria for discontinuation of protocol therapy include:

• Disease progression: Where disease progression is: the development of a new metastatic lesion or an objective status of disease progression (as defined by RECIST criteria) on two consecutive evaluations at least 6 weeks apart (Section 13.2).

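### Section 16.34 starts PFS at a randomization the trial does not have and leaves the progression date open between two scans 42 days apart, most naturally the later one

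*Combined protocol and SAP*

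**What the plan says.** Section 16.34 gives PFS as "Time from randomization to the first 2 consecutive evaluations approximately 6 weeks apart documenting disease progression", to be estimated by Kaplan-Meier. Section 16.35 gives overall survival as "Time from registration to death due to any cause". Sections 5.0 and 7.2 describe sequential run-in schedules followed by a continuation cohort, and 16.2 tests one cohort against a fixed null rate. No section allocates patients at random.

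On progression, 11.1 states: "Disease progression for this protocol is defined as meeting the RECIST criteria for disease progression on two consecutive evaluations at least 6 weeks apart". Footnote 8 of the test schedule in 4.1 says that, for a patient with PD who stays on treatment, "the next imaging should take place two cycles after the imaging showing PD". Section 7.0 sets the interval: "Cycle length is 21 days with the exception of Cycle 1" (Cycle 1 may run 7 days longer).

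The only sentence that assigns a date to progression is in 11.32, FDG-PET item b.ii. It covers a patient with no baseline FDG-PET whose positive follow-up PET is not matched by a new site on CT at the same evaluation: "In this situation, the date of PD will be the date of the initial abnormal PDG-PET scan".

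Two kinds of progression skip the second evaluation. The exception placed between 13.2 and 13.3 reads: "Patients who develop PD in the CNS should discontinue study treatment and go to Event Monitoring". Section 11.45 classes symptomatic deterioration as PD without objective evidence at that time. Section 16.34 mentions neither of these, nor death.

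**The concern.** Median PFS is a stated secondary objective (2.22), so an analyst needs one origin and one event date per patient. Section 16.34 supplies an origin that does not exist and an end that is two dates rather than one.

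A pair of evaluations is complete only at its second member, and under 11.1 the protocol's own progression criterion is not met until then. Followed literally, the text therefore leads to the confirming scan. Confirmation should settle whether a progression is real. Using it to settle when the progression happened adds the confirmation interval to the endpoint.

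Three consequences follow. The reported median may depend on a choice made after the data are seen. Confirmed and never-confirmed progressions would enter one curve under different dating rules. A patient who dies without two PD evaluations has, read literally, no PFS event at all.

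The date could also spill over into the PD-L1 comparison in 2.32 and 16.4, which splits patients by being progression-free and on study for at least 6 months. If that split uses the PFS date, a first PD scan at the end of Cycle 8 (8 × 21 = day 168) and its confirmation at the end of Cycle 10 (10 × 21 = day 210) fall on opposite sides of about 182 days.

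**Working it through.** **The plan's own figure.** The documents give no target, assumption or sample size for PFS. The only design calculation is for response rate (16.2): 33 patients, 12% versus 30%, one-sided 0.10. It reproduces. Rejecting at 7 or more responses gives exact alpha 0.093 and power 0.906. PFS dating does not enter it.

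**Size of the open interval.** Inputs: the confirming scan comes two cycles after the first PD scan (4.1, footnote 8; also 13.2), and a cycle is 21 days (7.0).

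- Gap = 2 × 21 = 42 days = 6 weeks.
- Earliest scheduled PD scan, end of Cycle 4: 4 × 21 = day 84. Its confirmation, end of Cycle 6: 6 × 21 = day 126.
- A 7-day extension of Cycle 1 moves both dates and leaves the gap unchanged.

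The shift per scan-confirmed progression is therefore 42 days if the second scan dates the event and 0 if the first does.

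**Effect on the median (illustration).** Assumptions, none from the documents: exponential progression times with true median *m* weeks, all scans on schedule at weeks 12, 24, 36 and so on, and every progression confirmed. The probability of having progressed by week *s* is 1 − 2^(−s/m). The recorded median is the first scan at which this reaches 0.5, plus 6 weeks if the confirming scan is used.

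| Assumed *m* (weeks) | By week 12 | By week 24 | By week 36 | Median, first scan | Median, confirming scan |
|---|---|---|---|---|---|
| 10 | 0.565 | – | – | 12 | 18 |
| 16 | 0.405 | 0.646 | – | 24 | 30 |
| 22 | 0.315 | 0.531 | – | 24 | 30 |
| 30 | 0.242 | 0.426 | 0.565 | 36 | 42 |

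**Progressions that skip confirmation.** If a share *f* has no confirming scan, the mean shift is 6 × (1 − f) weeks: 6.0 at f = 0, 4.8 at f = 0.2 and 3.0 at f = 0.5. The values of *f* are assumed.

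**The case against.** The strongest reply is that 16.34 never names the second scan. The text can be read either way, and under a first-scan reading the delay is zero. The one dating rule in the protocol also points to the initial scan. This stands in part: the demonstrated defect is an undefined date, and the confirming scan is only the more natural reading. Item b.ii does not settle the matter, because it decides whether one unmatched PET finding counts as progression and does not address the two-evaluation requirement in 11.1. For the same reason it should not be called an opposite convention for PET-detected progression in general.

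A reader might infer that every progression is recorded 6 weeks late. The documents do not support that. CNS progression and symptomatic deterioration need no confirming scan, and the wording of 13.3 leaves unclear whether a new metastatic lesion needs a second evaluation (13.3 and 13.2 must be reconciled on this).

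A reader might also infer that PFS here would be inflated against the 22 weeks quoted in 1.2. Section 1.2 does not say how progression was dated in that study, and the protocol plans no comparison with it.

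The percentage inflation depends wholly on assumed medians. The 12-week scan spacing can distort the median more than the disputed dating does: an assumed 16 weeks is recorded as 24 even under first-scan dating, and rewording 16.34 does not change that.

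Finally, the wrong origin may be only a slip, since 6.1 calls the enrolment system a registration/randomization application. That is plausible, but the word still has to be corrected. Treatment may start up to 7 days after registration (6.6), so the intended origin should not be left to inference.

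**Conclusion.** The point holds as a defect in the definition of a secondary, descriptive endpoint. Two parts are certain: the origin in 16.34 does not exist in this trial, and the event date is not fixed between two scans 42 days apart. That the text means the confirming scan is the most natural reading together with 11.1, but it is not stated.

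If the confirming scan is used, each scan-confirmed progression is dated about 6 weeks after RECIST PD was first met, and the recorded median can rise by about 6 weeks. The medians of 12 versus 18 and 24 versus 30 weeks are illustrations that assume exponential times, on-schedule scans and confirmation of every progression. The shift is smaller on average where some progressions are never confirmed. The omission of death and the lack of a rule for unconfirmed PD belong to the same repair. The primary endpoint and its sample size are not affected.

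**What to change.** Replace the definition in 16.34 with wording such as:

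> Time from registration to the earlier of death from any cause or disease progression, where a confirmed progression is dated at the first of the two consecutive evaluations that document it, whatever the imaging modality.

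Add two statements:

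- CNS progression and symptomatic deterioration count as events on the date they are documented.
- How a single PD evaluation that is never confirmed is counted, covering separately the patient who dies, the patient who stops before the second scan, and the patient whose second scan does not show PD.

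The cost is a few sentences in the protocol, best settled before PFS data are examined. The confirmation requirement, the treatment rules and the N = 33 design stay as they are. The downside is that the reported median PFS may be shorter than under confirming-scan dating.
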